11.3 INTERIM ANALYSES

Safety lead-in

Safety and tolerability data will be reviewed on a cohort-by-cohort basis during safety lead-in to determine if an additional cohort of patients should be enrolled at the current DL, if de-escalation is warranted, or if the protocol should be amended to evaluate additional intermediate or lower DLs. The final determination of the RP2D_c will be based on the totality of data including, but not limited to, safety and early signs of anti-tumor activity.

Dose expansion

Interim futility analysis. Given the limited sample size, there will be no futility interim analysis in the dose expansion cohort.

Continuous safety monitoring. Bayesian toxicity monitoring will be used to perform continuous safety monitoring of patients enrolled in the expansion cohort. Specifically, patients enrolled in the expansion cohort will be monitored for incidence of DLT-equivalent (DLT-E) events, defined as any safety event that would have qualified as a DLT had that patient been enrolled in the safety lead-in portion of the study. We assume the true DLT-E rate follows a beta (0.5, 0.5) prior distribution and, conditional on the true DLT-E rate, the number of patients who experience a DLT-E follows a binomial distribution. If $\text{Prob}(\text{DLT-E rate} > 33\% | \text{observed no. DLT-Es}) > 50\%$, trial enrollment will be paused. (Note: The observed number of DLT-Es will include DLTs from eligible safety lead-in patients treated at the RP2D_c who are included in the expansion cohort. Bayesian toxicity monitoring parameters were selected to calibrate with the 3+3 de-escalation rules used in the safety lead-in.) If the trial is paused, the safety review committee will review the totality of the safety data and determine whether to continue patient enrollment at the current RP2D_c, introduce intermediate or lower dose levels for evaluation, or close the trial to accrual and declare the combination of tarloxitinib and sotorasib too toxic. This monitoring rule has a 13% and 95% probability of pausing if the true DLT-E rate is 10% or 50%, respectively. The table below specifies safety monitoring thresholds.

Bayesian toxicity monitoring boundaries		
No. of patients	No. of DLT-Es to pause study	Observed DLT-E rate
6	≥2	≥0.33
7-9	≥3	≥0.33
10-11	≥4	≥0.36
12 – expansion cohort fully accrued		

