6.2 DEFINITION OF DOSE-LIMITING TOXICITY (DLT)

Toxicities will be graded according to the NCI Common Toxicity Criteria scale version 5.0. If multiple toxicities are seen, the presence of DLT should be based on the most severe toxicity grade experienced. DLT will be defined as any of the following events occurring during treatment with study drugs and is deemed possibly, probably or definitely attributable to the study drugs:

- Any Grade 3 or 4 thrombocytopenia, anemia and/or neutropenia.
- Any other non-hematologic Grade 3 or 4 toxicity that is clinically significant, excluding alopecia.
- Any grade 3 nausea, vomiting or diarrhea that persists > 72 hours despite the use of maximal medical intervention and/or prophylaxis as indicated by good clinical practice and the judgment of the investigator.
- Any grade 4 vomiting or diarrhea regardless of duration.
- Failure to recover from toxicities to be eligible for re-treatment within 4 weeks.
- Any death not clearly due to the underlying disease or extraneous causes, and for any toxicity requiring permanent discontinuation of study drug(s).
- Hy's law, defined as: AST or ALT > 3 x the upper limit of normal (ULN) with concurrent increase in total bilirubin > 2 x ULN without evidence of cholestasis or alternative explanations, (e.g., viral hepatitis, disease progression in the liver, etc.)
- Neutropenic fever

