Grade 4 TdP or polymorphic ventricular tachycardia, signs/symptoms of serious arrhythmia	
 Place patient on telemetry and obtain ECGs as clinical indicated Obtain Cardiologist consult and admit to hospital for extended observation on telemetry Permanently discontinue tarloxitinib

ECG = electrocardiogram; msec = millisecond; QTcF = corrected QT interval as calculated according to Fridericia's formula; TdP = Torsade de Pointes

Note: If QTcF prolongation is \geq Grade 3, an ECG may need to be repeated more frequently during the patient's visit depending on the degree of the prolongation and per institutional standards.

Treatment and retreatment guidelines in this study are based on absolute QTcF observations that vary from the NCI CTCAE. Importantly, dose reductions are not based on the QTcF change from baseline, only the absolute QTcF. For example, if a patient has a change > 60 msec from baseline but has an absolute QTcF ≤ 500 msec, no dose reduction is required.

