11.1.1 SAMPLE SIZE DETERMINATION

The sample size of 6 patients in the safety lead-in and 12 patients in the expansion cohort will allow for preliminary assessment of safety and anti-tumor activity at the RP2D_c. For primary safety outcomes, the table below shows the probability of observing at least one DLT/DLT-equivalent (DLT-E) for true DLT/DLT-E rates ranging from 10% to 40% for group sample sizes of 6 (safety lead-in cohort) and 12 (expansion cohort). (A DLT-equivalent is any safety event that would have qualified as a DLT had that patient been enrolled in the safety lead-in portion of the study.)

Probability of observing at least 1 DLT/DLT-equivalent events for n = 6 or 12.

True DLT/DLT-E rate	Probability of observing ≥ 1 DLT/DLT-Es	
	n=6	n=12
0.05	0.26	0.46
0.10	0.47	0.72
0.15	0.62	0.86
0.20	0.74	0.93
0.25	0.82	0.97
0.30	0.88	0.99

For the 12 patients in the expansion cohort, example incidence rates and corresponding exact 95% binomial confidence intervals (CIs) summarizing safety (e.g., AE or DLT-E rates) or response (e.g., ORR or DCR) are shown in the table below. The values are provided as a reference for estimation rather than as a basis for any decision criteria. The RP2D_c may be revised based on accumulated safety data obtained in expansion.

Estimated incidence rate and exact binomial 95% CI for n = 12.

No. of Cases	Estimated Rate	95% CI	
		Lower Limit	Upper Limit
0	0	0	0.26

1	0.08	0.00	0.38
2	0.17	0.02	0.48
3	0.25	0.05	0.57
4	0.33	0.10	0.65
5	0.42	0.15	0.72
6	0.5	0.21	0.79

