13 ADVERSE EVENT REPORTING REQUIREMENTS

13.1 PURPOSE

AE data collection and reporting, which are required as part of every clinical trial, are done to ensure the safety of patients enrolled in the studies as well as those who will enroll in future studies using similar agents. AE are reported in a routine manner at scheduled times during a trial. Additionally, certain AEs must be reported in an expedited manner to allow for more timely monitoring of patient safety and care. The following guidelines prescribe routine and expedited AEs reporting for this protocol.

Throughout the study, the Investigator will be required to provide appropriate information concerning any findings that suggest significant hazards, contraindications, side effects, or precautions pertinent to the safety of the drug under investigation.

Note: All deaths on study require both routine and expedited reporting regardless of causality. Attribution to treatment or other cause must be provided.

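### In expansion, 11.3 requires a pause and committee review only at a DLT-E count boundary, which one possibly drug-related death or torsades cannot reach by itself

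*Combined protocol and SAP*

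**What the plan says.** Section 11.3 (Dose expansion, continuous safety monitoring) states that "patients enrolled in the expansion cohort will be monitored for incidence of DLT-equivalent (DLT-E) events". With a Beta(0.5, 0.5) prior, enrolment pauses when the posterior probability that the DLT-E rate exceeds 33% is above 50%. The table turns this into counts: 2 or more at 6 patients, 3 or more at 7–9, 4 or more at 10–11. At 12 patients accrual is complete. DLTs in eligible lead-in patients treated at the RP2D_c are included. Committee review depends on the pause: "If the trial is paused, the safety review committee will review the totality of the safety data".

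Section 6.2 defines the events in one unweighted list. It includes "Any death not clearly due to the underlying disease or extraneous causes", "Any Grade 3 or 4 thrombocytopenia, anemia and/or neutropenia" and "Any other non-hematologic Grade 3 or 4 toxicity that is clinically significant, excluding alopecia". Torsades enters as a Grade 4 non-hematologic toxicity, and also because 6.5.4 makes it a reason to stop tarloxotinib for good.

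Four other provisions bear on such an event:

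- 6.5.4, Grade 4 row: telemetry, then "Obtain Cardiologist consult and admit to hospital for extended observation on telemetry", and permanent discontinuation of tarloxotinib.
- 13.1: "All deaths on study require both routine and expedited reporting regardless of causality", with an attribution.
- 11.1.1: "The RP2D_c may be revised based on accumulated safety data obtained in expansion".
- 11.3, Safety lead-in: safety data are reviewed cohort by cohort. This covers the lead-in only.

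**The concern.** A rule that counts DLT-Es answers one question: is the overall rate too high? It does not ask whether a single event is grave enough to stop and look. In expansion the plan attaches trial-level action (an enrolment pause and committee review) to the first question only.

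The plan itself foresees the hazard. QTc prolongation has the highest percentages in the tarloxotinib monotherapy column of 3.1.7 (60.9% any grade, 34.8% in the >G3 column), and 6.5.4 has a row for torsades. If 11.3 is followed to the letter, a further expansion patient may start the same dose after a possibly related death or torsades, before this document obliges anyone to decide whether that dose is still acceptable.

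**Working it through.** **Inputs.** From 11.3: prior Beta(0.5, 0.5), cutoff 33%, trigger 50%, boundaries 2 (n=6), 3 (n=7–9), 4 (n=10–11). From 11.1: a level passes with 0 or 1 DLT in 6, and expansion reaches 12 patients including eligible lead-in patients. I take all six lead-in patients as eligible, so they are patients 1–6, with cycle-1 events only.

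**Step 1: reproduce the plan.** With k events in n patients the posterior is Beta(0.5+k, 0.5+n−k). The smallest k with Prob(rate > 0.33) > 0.50 is 2 at n=6, 3 at n=7–9 and 4 at n=10–11, as tabled. An exact sequential binomial calculation over n=6 to 11 gives pause probabilities of 12.6% at a true rate of 10% and 95.0% at 50%, against the stated 13% and 95%. The plan's arithmetic is right.

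**Step 2: posterior Prob(rate > 33%) for small counts.**

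| n | k=1 | k=2 | k=3 |
|---|---|---|---|
| 6 | 0.204 | 0.528 (pause) | – |
| 7 | 0.145 | 0.421 | 0.720 (pause) |
| 8 | 0.102 | 0.330 | 0.621 (pause) |
| 9 | 0.072 | 0.255 | 0.525 (pause) |
| 10 | 0.050 | 0.195 | 0.436 |
| 11 | 0.035 | 0.147 | 0.356 |

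One event never pauses at any tabled n. After a 0/6 lead-in, two related deaths among patients 7–9 make k=2 and do not pause. After 1/6, the same two deaths make k=3 and do pause; if the second falls in patient 10 or 11, k=3 does not.

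**Step 3: what the count rule does after a level has passed.** At a 10% rate, P(0 of 6) = 0.9^6 = 0.531 and P(1 of 6) = 6 × 0.1 × 0.9^5 = 0.354. The n=6 look therefore supplies 1 − 0.531 − 0.354 = 0.114 of the 0.126, and the 3+3 rule has already made that look. Given a passed level, the pause probability over patients 7–11 is (0.1257 − 0.1143)/0.8857 = 0.013.

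**Step 4: effect of a single-event trigger on the same basis.** Let q be the assumed severe-event rate, taken as part of the 10% DLT-E total. Start from 0 or 1 events with weights 0.60 and 0.40 (0.531/0.886 and 0.354/0.886). For each of patients 7–11, a severe event (probability q) pauses, an ordinary DLT-E (0.10 − q) adds one to the count, and the boundaries apply as tabled.

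| Assumed q | Severe event in five patients, 1 − (1−q)^5 | Pause, count rule alone | Pause, with trigger |
|---|---|---|---|
| 1% | 4.9% | 1.3% | 5.9% |
| 2% | 9.6% | 1.3% | 10.4% |
| 5% | 22.6% | 1.3% | 22.9% |

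**Step 5: how often the existing rule would catch a first severe event.** Given a passed level and q = 5%, the first severe event in patients 7–11 before any pause crosses no boundary in 99%, 94% and 88% of cases at total DLT-E rates of 10%, 20% and 30%. With the total at 20% and q at 3% or 1%, the figures are 93% and 92%.

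**The case against.** **A count rule is a legitimate choice.** The rule is fully specified, deliberately calibrated to the 3+3, and its operating characteristics are correct. No count rule reacts to one event once the denominator has grown. All of that stands; nothing in 11.3 is miscalculated.

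**A reader might infer that all action on such an event is discretionary.** The documents do not support this. For torsades, telemetry, cardiology consult, admission and permanent discontinuation of tarloxotinib are required. For deaths, expedited reporting and attribution are required. Only trial-level action is left open.

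**A reader might infer that deaths cannot pause the trial.** That is also too strong. A death can complete a boundary when earlier DLT-Es exist, as Step 2 shows after a 1/6 lead-in.

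**A reader might take 34.8% as a sign that torsades is likely.** It is a rate of QTc prolongation, not torsades. The plan also guards against torsades: pre-infusion QTcF below 450 msec and potassium of at least 3.5 mEq/L (6.5), dose reduction at 501–600 msec and a permanent stop from 601 msec (6.5.4), and ECGs around every infusion (9.2). Clinically significant Grade 3 QTc events already count as DLT-Es.

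**The sizes rest on assumed rates.** This stands. The severe-event column in Step 4 is little more than the assumed rate over five patients. It does not show that harm is probable.

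**Other safeguards may exist.** The committee's charter is not in this document, and IRB oversight applies (15.2). Either may call for ad hoc review, and the investigator can always stop enrolment. The finding is therefore limited to what this document requires.

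**Conclusion.** The point holds as a cheap improvement, not as an error. In expansion, a pause and committee review are mandatory only at a count boundary, and one possibly drug-related death or torsades does not reach one at any n from 6 to 11 (0.204 falling to 0.035 against 0.50). That result needs no assumed event rate. It does assume that all six lead-in patients at the RP2D_c are eligible and counted; the formula would pause on one event only at n=1–3 (0.910, 0.712, 0.536), below the first tabled row.

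At most six patients are added after a fully eligible lead-in. A pause can protect those who have not yet started when the event occurs. The lead-in is outside this point because its data are already reviewed cohort by cohort.

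One ambiguity could widen the gap. Section 6.2 speaks of events during treatment, while 11.1.2 sets a 28-day DLT-observation period. If the shorter window governs DLT-Es, a death after cycle 1 would not enter the count at all.

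**What to change.** Add to 11.3, Dose expansion, wording such as: *Whatever the DLT-E count, any death at least possibly related to study drug, or any Grade 4 QTc event per 6.5.4 (torsades, polymorphic ventricular tachycardia, signs or symptoms of serious arrhythmia), in a patient enrolled after the RP2D_c is declared pauses enrolment until the safety review committee has reviewed it.*

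Using the whole Grade 4 row is wider than torsades alone, but it avoids a new definition. Leave the count boundaries as they are. Keep 13% and 95% as properties of the count rule alone, and add a note that the extra trigger raises the pause probability by an amount that depends on the assumed severe-event rate. No single replacement values exist without such a rate.

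The text change is a sentence and a note, using the existing committee. The operating cost is more short pauses: from 1.3% to 5.9%, 10.4% or 22.9% in the Step 4 setting. Because 13.5 lets an event count as possibly related when concurrent disease could also explain it, some pauses will be for deaths later judged due to disease. Each lasts only until the committee has reviewed the event.

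As worded, the trigger does not cover late events in lead-in patients carried into expansion. The sponsor could extend it to them, but the pause figures above would then be too low.

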11 STATISTICAL CONSIDERATIONS

11.1 STUDY DESIGN

Study CTO # 103048 is a potentially multicenter, non-randomized, single cohort phase IB trial evaluating the safety and efficacy of tarloxotinib in combination with sotorasib in NSCLC patients with KRAS G12C mutation who have progressed on any small molecule KRAS G12C inhibitor.

Safety lead-in

A minimum of 6 patients and as many as 18 patients will be enrolled in a safety lead-in cohort to evaluate the safety of the combination of tarloxotinib and sotorasib. Sotorasib will be held at a fixed dose of 960 mg QD (the approved dose) while the starting dose of tarloxotinib will be the monotherapy RP2D equal to 150mg/m² QW (dose level 1 [DL1]). Following a 3+3 algorithm, an initial 3 patients will be enrolled at DL1. If 0 or 1 of 3 patients experience a DLT, an additional 3 patients will be enrolled to DL1. DL1 will be declared the combination RP2D (RP2D_c) if at most 1 of 6 patients treated at DL1 experience a DLT. Alternatively, if there are 2 or more DLTs observed at DL1, 3 patients will be enrolled at DL -1 and the 3+3 rules repeated for safety evaluation. The RP2D_c will be the highest DL at which at most 1 patient of 6 experiences a DLT. If DL -2 is considered too toxic, additional dose levels below DL -2 to be determined may be considered for safety.

Dose expansion

Once the tarloxotinib RP2D_c is reached, an expansion cohort of up to 12 patients will be enrolled to evaluate the safety of the combination of tarloxotinib and sotorasib. Eligible safety lead-in patients treated at the RP2D_c will be included in the expansion cohort.

The combination of tarloxotinib and sotorasib will not be considered promising if there is weak evidence the true objective response rate (ORR) exceeds 20%. Specifically, the trial will be declared negative if $\text{Prob}(\text{true ORR} > 20\% | \text{observed no. of responses}) < 20\%$, equivalent to observing at most 1 response in 12 patients. We assume the true ORR follows a beta (0.5, 0.5) prior distribution and, conditional on the true ORR, the number of responses follows a binomial distribution. If at least 2 responses in 12 patients are observed, the combination may be considered promising. Given 1 response in 12 patients, the probability the true ORR exceeds 20% is approximately 16%. Given 2 responses in 12 patients, the probability the true ORR exceeds 20% is approximately 42%.

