11.1.2 POPULATIONS FOR ANALYSES

The following analysis sets will be defined for this study.

The **safety analysis set** comprises all enrolled patients who receive any quantity of study treatment, regardless of eligibility. The safety evaluation will be performed based on the first dose of study treatment a patient receives, regardless of the patient's cohort assignment. The safety analysis set will be used for all dosing/exposure and safety analyses.

The **DLT-evaluable population (safety lead-in only)** comprises patients who have either completed the DLT-observation period (1 cycle, 28 days) and received at least 75% of planned doses of the tarloxotinib and sotorasib combination in cycle 1 or have discontinued study treatment or study participation before completing cycle 1 due to a DLT.

The **intention to treat (ITT) analysis set** comprises all patients in the safety analysis set eligible for study inclusion and who meet the inclusion criteria for dose expansion, including eligible safety lead-in patients treated at the RP2D_c. This analysis set will be used for all efficacy analyses.

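### Section 11.3 gives 13% and 95% as the pausing probabilities of expansion monitoring, but most of both figures is the n=6 lead-in decision; given a passed lead-in with all 6 carried forward and no later event counted in them, they are about 1% and 54%

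*Combined protocol and SAP*

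**What the plan says.** Section 11.3, under Dose expansion, introduces the rule as follows: "Bayesian toxicity monitoring will be used to perform continuous safety monitoring of patients enrolled in the expansion cohort". Enrolment is paused when the posterior probability that the DLT-equivalent (DLT-E) rate exceeds 33% is above 50%, under a beta(0.5, 0.5) prior. The table gives boundaries of 2 or more events at n=6, 3 or more at n=7 to 9, and 4 or more at n=10 to 11. There is no boundary at n=12, when the cohort is full. One sentence gives the operating characteristics: "This monitoring rule has a 13% and 95% probability of pausing if the true DLT-E rate is 10% or 50%, respectively".

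A note in the same paragraph says "The observed number of DLT-Es will include DLTs from eligible safety lead-in patients treated at the RP2D_c" and "Bayesian toxicity monitoring parameters were selected to calibrate with the 3+3 de-escalation rules used in the safety lead-in".

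Section 11.1 sets the lead-in rule. A level becomes the combination RP2D if at most 1 of 6 patients has a DLT; otherwise, "if there are 2 or more DLTs observed at DL1, 3 patients will be enrolled at DL -1". On the expansion cohort of up to 12 it says: "Eligible safety lead-in patients treated at the RP2D_c will be included in the expansion cohort".

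**The concern.** A reader of section 11.3 will take 95% as the chance that monitoring pauses enrolment once expansion has opened at a level with a 50% DLT-E rate. But the first row of the table is the same cut as the lead-in rule, applied to the same patients. If all 6 are carried forward and no further event is counted in them, a level with 2 or more events in 6 never reaches expansion, so that row cannot trigger a pause there.

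This pair is the only operating characteristic given for the rule. The safety review committee and the IRB need to know how much protection the rule adds after the lead-in, and section 11.3 does not let them see it.

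**Working it through.** **Inputs.** Prior, criterion and boundaries are from the section 11.3 table and text. The condition for opening expansion (at most 1 DLT in 6) and the carrying forward of lead-in patients are from section 11.1. True rates p are 10% and 50%, as in section 11.3.

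**1. Boundaries.** With x events in n patients, the posterior is beta(0.5 + x, 0.5 + n − x). P(rate > 0.33) is:

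| n | one event below boundary | at boundary |
|---|---|---|
| 6 | 0.204 (x=1) | 0.528 (x=2) |
| 7 | 0.421 (x=2) | 0.720 (x=3) |
| 9 | 0.255 (x=2) | 0.525 (x=3) |
| 10 | 0.436 (x=3) | 0.691 (x=4) |
| 11 | 0.356 (x=3) | 0.607 (x=4) |

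The tabled boundaries are correct.

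**2. The n=6 decision.** P(at most 1 of 6) = (1−p)^6 + 6p(1−p)^5.

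- p=0.1: 0.5314 + 0.3543 = 0.8857, so P(2 or more of 6) = 0.1143.
- p=0.5: 1/64 + 6/64 = 0.1094, so P(2 or more of 6) = 0.8906.

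**3. Pause after n=6, starting from k events in 6.** A pause needs a total of 3 by patient 9, or a total of 4 by patient 11.

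- From k=1: P(2 or more of 3) + P(exactly 1 of 3) × p².
  - p=0.1: 0.028 + 0.243 × 0.01 = 0.0304.
  - p=0.5: 0.5 + 0.375 × 0.25 = 0.5938.
- From k=0: P(3 of 3) + P(exactly 2 of 3) × p².
  - p=0.1: 0.001 + 0.027 × 0.01 = 0.0013.
  - p=0.5: 0.125 + 0.375 × 0.25 = 0.2188.

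**4. Pause in expansion, given at most 1 DLT in 6.** The weights on k=0 and k=1 are the two terms in step 2 divided by their sum.

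- p=0.1: 0.600 × 0.0013 + 0.400 × 0.0304 = 0.0129.
- p=0.5: (1/7) × 0.2188 + (6/7) × 0.5938 = 0.5402.

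**5. Reproducing the plan's figures.** Total = n=6 decision + P(pass) × conditional pause.

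| True rate | n=6 decision | added at n=7 to 11 | total | plan states |
|---|---|---|---|---|
| 10% | 0.1143 | 0.8857 × 0.0129 = 0.0115 | 0.1257 | 13% |
| 50% | 0.8906 | 0.1094 × 0.5402 = 0.0591 | 0.9497 | 95% |

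The plan's figures are reproduced by counting from the first lead-in patient with looks at n=6 to 11. At p=0.5, a level passes the lead-in and is never paused with probability 0.1094 × 0.4598 = 0.0503, which is 1 − 0.9497.

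**6. Sensitivity to who is carried forward (p=0.5).** These cases change the 54%, and each needs an assumption that the documents do not supply.

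- Five carried forward, the excluded patient a random one of the six: 69%.
- Five carried forward, the excluded patient never the one with the DLT: (1/7) × 0.4063 + (6/7) × 0.7969 = 0.741.
- Five carried forward, all five DLT-free: 0.406.
- A seventh, event-free patient carried forward: (1/7) × 0.0625 + (6/7) × 0.375 = 0.330.
- No lead-in patient carried forward, contrary to section 11.1: 95%.

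**The case against.** The strongest reply is that nothing printed is wrong and the scope can be worked out. The sentence describes the rule; the rule's table starts at n=6; section 11.1 places eligible lead-in patients in the expansion cohort; and the note says their DLTs are counted and the parameters match the 3+3. All of that stands, and it is why this is a fault of labelling. It falls short because no sentence says that the two probabilities include a decision taken before expansion opens. A reader would have to redo the recursion to find that 89.1 of the 95.0 points are that decision.

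It can also be said that 54% is conditional and 95% is not, so one does not replace the other. That is right. At a 50% rate the lead-in is passed only 10.9% of the time. The two figures answer different questions and both should be given, each labelled.

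Three stronger readings may tempt a reader.

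- *That 13% and 95% are miscalculated.* They reproduce exactly.
- *That patients are less well protected than claimed.* With all 6 carried forward, the combined probability is still 12.6% and 95.0%.
- *That a range of expansion figures for 4, 5 or 6 carried forward can be printed as fact.* The documents do not say how ineligibility relates to DLT status. With 5 carried forward at a 50% rate, the result runs from 41% to 74% on that point alone.

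Whether later events in lead-in patients count is a separate question. Section 6.2 sets no time limit ("DLT will be defined as any of the following events occurring during treatment with study drugs"), while section 11.1.2 describes "patients who have either completed the DLT-observation period (1 cycle, 28 days". Counting later events would move more of the pausing into expansion, but the documents give no share of events falling after cycle 1 from which to compute it.

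**Conclusion.** The point holds as a labelling fault in the only operating characteristic given for the expansion rule. The stated 13% and 95% are the probability that a single dose level is rejected in the lead-in or paused in expansion. The n=6 decision supplies 11.4 and 89.1 points; looks at n=7 to 11 add 1.1 and 5.9. Given a passed lead-in, the pause probability during expansion is about 1% and 54%.

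The conditional pair assumes that the level was declared by the at-most-1-in-6 rule, that exactly those 6 patients are carried forward, and that no later event is counted in them. The first is an approximation, because section 11.3 also bases the final choice of dose on the totality of the data. Neither the boundaries nor overall protection is in doubt, and a pause leads to committee review, not automatic closure. The correction is worth making because it changes what the committee and IRB would believe about monitoring after the lead-in.

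**What to change.** In section 11.3:

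1. Replace the operating-characteristic sentence with: *The probability that a single dose level is rejected in the lead-in or paused in expansion is 13% and 95% if the true DLT-E rate is 10% or 50%, with all 6 lead-in patients carried forward.*
2. Add: *Given at most 1 DLT in 6 in the lead-in, all 6 carried forward and no later event counted in them, the probability of a pause during expansion is about 1% and 54%; it differs if another number is carried forward or later events are counted.*
3. Note under the table that the n=6 row normally coincides with the lead-in decision.

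Leave figures for other numbers carried forward, or for later events, out of the protocol unless their assumptions are printed beside them. Reconcile the DLT time window in sections 6.2 and 11.1.2 as a separate point.

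The cost is one relabelled sentence, one added sentence and a table note. Boundaries, decision rule and enrolment do not change. The downside is that the figure stated for expansion at a 50% rate becomes less favourable.
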